All UC Davis ED patients who are being evaluated for ILI or URI by an ED physician and who agree to having a nasopharyngeal swab sample collected for the study will be eligible for recruitment. Since this procedure poses minimal risk to individuals and no risks to an embryo or fetus should the patient be or become pregnant, we will not exclude pregnant women from this study.

Our study will also include children (individuals below 18 years old) since the collection of the nasopharyngeal swab sample poses minimal risk to them. Informed consent will be obtained from the children's parents, legally authorized representative or guardian before the child is enrolled. In addition, should an adult be incapable of giving informed consent, consent will be obtained from the individual's legally authorized representative.

Spanish speaking patients will also be included. We plan to translate our informed consent documents into Spanish after IRB approval and a translator will be present in the ED to allow proper communication between the patient and ED research coordinators, ED nurse, or physician throughout the study. Other non-English speaking patients will be excluded.

We will also exclude those patients who are prisoners or are currently taking antibiotic or antiviral medications.

5) Study Timelines

The study will begin upon IRB approval and continue until December 2017. Eligible patients will be identified by ED research coordinators or EMRAP students and will be approached by ED Research Coordinators and asked for consent to enroll. The patient will continue to be a part of the study throughout their time in the ED. Additional follow up data collection and analysis of results will be performed for 1-5 years after completion of the active enrollment phase.

6) Study Endpoints

Patients may be recruited until the end of December 2018 while primary data analysis will be

PROTOCOL TITLE: Pilot randomized clinical trial of multi-respiratory pathogen testing versus usual care in emergency department (ED) patients with upper respiratory symptoms

completed within one year after patient recruitment ends.

7) Procedures Involved

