All UC Davis ED patients who are being evaluated for ILI or URI by an ED physician during the study period will be eligible for recruitment. Once the ED research coordinator or EMRAP students identify an eligible patient, the patient will be approached by the ED Research Coordinator and asked for consent to enroll. After obtaining informed consent, patients will be randomized to one of two arms: multi-respiratory pathogen testing together with usual care or clinician directed standard of care (which may include but is not limited to no testing or targeted influenza molecular testing *Alere I Influenza A & B*) using a simple randomization scheme. In this study, the randomization scheme we are planning to use is individual randomization. To ensure that the study population includes patients treated as outpatients vs. admitted, patients will be recruited from the 'up front care' treatment area (urgent care unit for ED patients expected to be treated as outpatients), in addition to our main emergency department area.

A brief demographic and symptom questionnaire will be administered to all subjects (see attachment). If patients are assigned into the control group, they will receive clinician directed standard of care (which may include but is not limited to no testing, point-of-care influenza molecular testing *Alere I Influenza A & B*, or multi-pathogen respiratory viral panel testing at off-site laboratory performed 3-4 times weekly in scheduled batches). Conversely, patients randomized to receive the rapid FilmArray RP, will receive usual care plus have a nasopharyngeal swab collected by an ED nurse or ED physician for FilmArray RP testing. The nasopharyngeal swab will be transported to the CLIA-certified clinical laboratory located one-floor above the ED where a licensed Clinical Laboratory Scientist (CLS) will perform the FilmArray RP test in real-time. Once the test is completed, FilmArray RP results will be reported in EMR via standard procedures and be available to ED physicians for use in patient management. ED physicians are free to decide how the test results will impact their treatment decisions and whether they would like to share these results with their patients. To ensure that results are available before ED physicians make treatment decision, we will encourage the ED triage physician to order the test before patients are put into ED rooms and ensure that FilmArray RP results are reported within 2 hours of sample collection.

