An ED research coordinator will be present to educate and clarify any questions or uncertainties the patients might have about the study before they sign the informed consent form. The ED research coordinator will also emphasize that none of the patient's identifiable information will be released and that all responses and results will be kept confidential and used for research purposes only. All patient enrollment, completion of the questionnaire and collection of the nasopharyngeal swab sample will be done in a private room in the ED.

17) Economic Burden to Subjects

As part of the agreement with BioFire Diagnostics, the UC Davis ED will be provided two FilmArray instruments and approximately 900 FilmArray respiratory panel reagent pouches. Hence, subjects who are assigned to the rapid, multi-respiratory pathogen testing will not incur any additional costs.

18) Consent Process

Once an eligible patient is identified, the patient will be approached by an ED Research Coordinator and asked for consent to enroll. Consent will occur after recruitment, but prior to any research activities. Consent will also occur face to face in a private room in the ED. Prior to obtaining consent, ED research coordinators will describe the study protocol and the possible risks and benefits and also address any questions or concerns the subject may have about the study. Patients will be provided with the IRB approved informed consent document to read given ample time to read the document and decide if they want to participate. After this point, eligible patients will sign the consent form. The signed consent form will be copied and the copy of the signed consent form will be given to the patient for personal records while the original will be kept by the ED Research Coordinator for the research record. After all research activities are completed, all data collected will be entered into a database. Hard copies of the consent forms and questionnaire will be stored in a lock box in a secure location in the ED. Contents of the lock

PROTOCOL TITLE: Pilot randomized clinical trial of multi-respiratory pathogen testing versus usual care in emergency department (ED) patients with upper respiratory symptoms

box will be collected by study personnel when necessary and transferred to a locked cabinet in the principal investigator's office.

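### Patients whose antibiotic or antiviral is already ordered at this visit can still be randomised, so the antibiotic effect may be diluted, and 152 per arm leaves no power in reserve

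*Combined protocol and SAP*

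**What the plan says.** All references are to the combined protocol and SAP.

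- **Aim on timing (Section 7, Procedures Involved).** The protocol sets its own standard: "To ensure that results are available before ED physicians make treatment decision". It names two means. Staff will "encourage the ED triage physician to order the test before patients are put into ED rooms", and the study will "ensure that FilmArray RP results are reported within 2 hours of sample collection".
- **Sequence (Section 7).** Recruitment is open to patients already under evaluation: "All UC Davis ED patients who are being evaluated for ILI or URI by an ED physician during the study period will be eligible for" entry to the study. Allocation follows consent: "After obtaining informed consent, patients will be randomized to one of two arms". Only then do FilmArray patients get the study swab; they "will receive usual care plus have a nasopharyngeal swab collected by an ED nurse or ED physician for FilmArray RP testing".
- **Related exclusion (Section 4).** "We will also exclude those patients who are prisoners or are currently taking antibiotic or antiviral medications".
- **Place (Section 16).** "All patient enrollment, completion of the questionnaire and collection of the nasopharyngeal swab sample will be done in a private room in the ED".
- **Power (Section 8, Power Analysis).** At least 152 patients per arm, 304 to 325 in total, are planned to detect a fall in antibiotic use from 40% to 25% with more than 80% power. No allowance for late results is stated.
- **Data on use of results (Sections 7 and 8).** Chart review will look at whether physicians knew of and used the results. Treatments before, during and after the episode and length of ED encounter will be collected. No comparison of result time with order time is described.

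**The concern.** The objective is the effect on treatment of having the result. A FilmArray patient whose antibiotic was ordered before the result appeared can hardly be influenced by it, but counts fully in that arm. The written procedures leave two openings.

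1. **Before randomisation.** An order placed earlier in the visit does not make the patient ineligible unless treatment has started.
2. **After randomisation.** The turnaround commitment starts at sample collection. The time from randomisation to swab is additional and has no limit, and physicians are not asked to wait.

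If either happens often, the trial loses power against the planned 15 points. A null finding would also be hard to interpret: the result may have come too late, or physicians may have had it in time and prescribed as before. For a pilot meant to guide larger trials, telling these apart is a main product. Dropping late-result patients from the analysis would break the randomised comparison, so the protection has to be applied before allocation.

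**Working it through.** **Inputs from Section 8.** Control rate p1 = 0.40, FilmArray rate p2 = 0.25, n = 152 per arm, power above 80%. The documents do not state alpha or sidedness; two-sided 0.05 is assumed.

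**Step 1: reproduce the plan's sample size.** Two proportions, pooled variance under the null, no continuity correction, mean rate 0.325:

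n = [1.96·√(2·0.325·0.675) + 0.8416·√(0.40·0.60 + 0.25·0.75)]² / 0.15²
= [1.2982 + 0.5503]² / 0.0225 = 151.9, so **152 per arm**.

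Power at n = 152 is Φ{[0.15 − 1.96·√(0.43875/152)] / √(0.4275/152)} = Φ{(0.1500 − 0.1053)/0.0530} = Φ(0.843) = **80.0%**. The plan's figure reproduces under these assumptions, with nothing to spare.

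**Step 2: dilution model.** Let f be the share of FilmArray patients whose antibiotic decision precedes the result. Assume that these patients get no effect and that the others get the full 15 points. The observed difference is then 15·(1 − f) points. The documents give no value for f, so a range is shown.

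| f (assumed) | FilmArray rate | Difference | Power, 152 per arm | n per arm for 80% |
|---|---|---|---|---|
| 0 | 25.0% | 15.0 points | 80.0% | 152 |
| 5% | 25.75% | 14.25 points | 75.6% | 170 |
| 10% | 26.5% | 13.5 points | 70.7% | 190 |
| 20% | 28.0% | 12.0 points | 59.9% | 244 |

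For f = 10%, the mean rate is 0.3325 and power = Φ{[0.135 − 1.96·√(0.44389/152)] / √(0.43478/152)} = Φ{(0.1350 − 0.1059)/0.0535} = Φ(0.544) = 70.7%.

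**Step 3: upper end of planned enrolment.** A total of 325 is about 162 per arm. Power is 82.5% at f = 0, falls below 80% at about f = 3%, and is 73.4% at 10% and 62.6% at 20%.

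**Step 4: the other control rate.** The same paragraph also anticipates 50% antibiotic use in controls. For 50% versus 35%, 152 per arm gives 75.6% power at f = 0 and 66.3% at f = 10%. That discrepancy is a separate matter, but it offers no reserve either.

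**The case against.** The protocol does address timing. It states the aim and commits to a turnaround. It also describes real-time testing one floor above the ED, with an assay of about an hour. The Section 4 exclusion can catch treatment already started at this visit. Physicians are free to use or ignore results, and in a pragmatic comparison late results are part of what offering the test delivers. Chart review of awareness and use would help to explain a null finding. The detection half of the first hypothesis does not depend on decision timing. The dilution model is simple: an order could be revised when a result arrives, and the planned 15 points might already allow for some late results.

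Most of this stands, and it limits the point. It does not close the two openings. An antibiotic ordered but not started is not clearly covered by the exclusion, and no analysis sets result time against order time.

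A reader might also infer that Sections 7 and 16 contradict each other, so that ordering before rooming cannot happen. The documents do not support that. Section 16 does not say where the private room is. It could be at triage, and the triage physician could be the ED physician who is evaluating the patient. The two passages need clarifying; they do not show an impossibility.

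**Conclusion.** The point holds as a gap in eligibility and timing that puts power at risk. Patients with an antibiotic or antiviral already ordered at this visit can be randomised, and the 2-hour target does not cover the time before sampling. At 152 per arm any dilution takes power below 80%: to 75.6%, 70.7% or 59.9% if 5%, 10% or 20% of FilmArray decisions come first.

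These figures rest on two-sided 0.05, a 40% control rate, no effect once the decision is made, and no allowance for late results within the 15 points. The shares are illustrative.

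Two stronger conclusions should not be drawn. One is that the effect will be diluted by a known amount: the documents give no time to decision, no ED length of stay and no share of late results. The other is that the comparison is biased: with all randomised patients analysed by assignment, it remains a fair estimate of the effect of offering the test.

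**What to change.** 1. **Section 4.** Add that a patient is not eligible if an antibiotic or antiviral has already been ordered or prescribed for this visit. The coordinator checks the EMR after consent and before randomisation, in the same way for both arms. Checking after consent and authorisation also respects the limits that Section 8 puts on chart entry.
2. **Sections 7 and 8.** Extract the times of randomisation, swab, result and first antibiotic or antiviral order. Keep every randomised patient in the main comparison. Report, descriptively, the share of FilmArray results posted before the first treatment order, and state how patients with no order are counted. This also covers orders placed between randomisation and result, which the eligibility check cannot prevent.
3. **Sections 7 and 16.** State where the private room lies in the patient's path and how it fits with ordering before rooming.

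**Cost.** Protocol wording, one chart check per consented patient and four extra data fields. Some patients identified late are lost, so recruitment is slightly slower. A decision not yet entered in the EMR will be missed. That the four times can be extracted is an assumption for the site to confirm; bulk extraction from the EMR and laboratory databases is already planned.

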PROTOCOL TITLE: Pilot randomized clinical trial of multi-respiratory pathogen testing versus usual care in emergency department (ED) patients with upper respiratory symptoms

1) Protocol Title:

Pilot randomized clinical trial of multi-respiratory pathogen testing versus usual care in emergency department (ED) patients with upper respiratory symptoms

Version Date: February 23, 2018

2) Objectives

To prospectively evaluate the effect of rapid, multi-respiratory pathogen molecular testing vs. usual care among patients being evaluated for influenza like illness (fever or cough and sore throat; ILI) and/or upper respiratory infection (nonspecific upper respiratory symptoms without fever; URI) in the emergency department (ED) setting. Specifically, we will evaluate the impact of having the rapid, multi-respiratory pathogen molecular test results on the frequency of respiratory pathogen detection, clinical treatment and outcomes among patients. To do so, we plan to conduct a prospective, patient-oriented, pilot randomized clinical trial of the BioFire FilmArray Respiratory Panel (FilmArray RP) from clinical nasopharyngeal swab viral transport media versus usual care (which may include but is not limited to no testing or targeted influenza molecular testing *Alere I Influenza A & B*).

Our study has two hypotheses:

- 1) Rapid, FilmArray RP testing will increase the proportion of ED patients with a specific respiratory virus detected and decrease the proportion of ED patients receiving unnecessary antibiotics for viral infection, relative to patients receiving usual care.
- 2) Rapid, FilmArray RP testing will increase the frequency of a confirmed influenza diagnosis and improve overall anti-influenza medication use (composite rate of anti-influenza treatment in positive patients and non-use of anti-influenza treatment in negative patients) in ED patients, relative to usual care.

3) Background

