In order to evaluate the impact of having rapid FilmArray RP results on clinical treatment, outcomes, and costs among ED patients, we will collect additional clinical and administrative data from EMR, laboratory, and UCDHS administrative databases. These data may include but are not limited to demographic characteristics, ICD10, CPT, and DRG diagnosis, procedure, and billing codes, charge and cost data, admission source, discharge disposition, clinical signs and symptoms of respiratory or other illness, relevant laboratory and radiology results, medications, antibiotics, antiviral and other respiratory treatments (e.g., oxygen, nebulizers and inhaled treatment) 30 days before, during, and after the ED episode of care, length of ED encounter, and data for any hospitalization, ED, or outpatient clinic visits within 30 days. These additional data collection and analysis of results will be performed for 1-5 years after completion of the active enrollment period (December 2017).

8) Data and/or Specimen Management and Confidentiality

PROTOCOL TITLE: Pilot randomized clinical trial of multi-respiratory pathogen testing versus usual care in emergency department (ED) patients with upper respiratory symptoms

Power Analysis - Based on existing literature and baseline data, we anticipate approximately 50% of patients with the diagnosis of ILI or viral URI in the control group will receive antibiotics, whereas 10% with confirmed influenza will receive antivirals. Based on the effect sizes, anticipating significant improvement in detection rates for influenza and other viral pathogens, and hypothesizing a 15 percentage point decrease in antibiotic use for patients with ILI or URI from 40 to 25% in the multi-respiratory pathogen test group, we plan to enroll approximately 304 – 325 patients over 12-18 months (June 2016 – December 2017). A sample size of at least 152 enrolled patients in each of the control and intervention arms will provide > 80% power to detect any true 15 percentage point difference between the multi-respiratory pathogen test and usual care arms.

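### The power statement leaves two control antibiotic rates (about 50% and 40%) unreconciled, and its claim of more than 80% power for any 15-point difference at 152 per arm fails for control rates between roughly 40% and 75%

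*Combined protocol and SAP*

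**What the plan says.** All the figures are in the Power Analysis paragraph of section 8 (Data and/or Specimen Management and Confidentiality).

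- First control rate: "we anticipate approximately 50% of patients with the diagnosis of ILI or viral URI in the control group will receive antibiotics".
- Second control rate, in the next sentence, as the hypothesised effect: a 15-point fall in "antibiotic use for patients with ILI or URI from 40 to 25% in the multi-respiratory pathogen test group".
- Enrolment, in the same sentence as the second rate: "we plan to enroll approximately 304 – 325 patients over 12-18 months".
- Power: "A sample size of at least 152 enrolled patients in each of the control and intervention arms" is said to be enough; it "will provide > 80% power to detect any true 15 percentage point difference between the multi-respiratory pathogen test and usual care arms".

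The paragraph gives no alpha, sidedness, test or allowance for loss. Elsewhere the outcome and the patients are worded differently. Hypothesis 1 in section 2 speaks of a test that will "decrease the proportion of ED patients receiving unnecessary antibiotics for viral infection", and section 7 makes eligible all "ED patients who are being evaluated for ILI or URI by an ED physician during the study period will be eligible for recruitment".

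**The concern.** There are two linked problems.

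First, consecutive sentences give control antibiotic rates of about 50% and 40%. The first is for patients with a diagnosis of ILI or viral URI, the second for patients with ILI or URI. The plan does not say whether these are different groups, or why the lower rate is the one used. The wording of hypothesis 1 and of the eligibility rule does not settle it.

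Second, the power sentence goes beyond the case that was calculated. The variance of a proportion grows as the rate nears 50%, so a fixed 15-point difference is harder to detect there. A sample size that only just reaches 80% at 40% vs 25% cannot hold 80% when both rates move towards the middle, and the plan's own first rate would move them that way.

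At stake is how a null antibiotic result would be read. The plan implies a type II error under 20%. At a control rate somewhat above 40% that is not what the design delivers. The control rate also matters beyond this trial, because section 3 says the results are to guide larger trials.

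**Working it through.** **Inputs from section 8:** 152 per arm (304 in total), upper enrolment 325 (325 / 2 = 162.5, taken as 162 per arm), difference d = 0.15, control rates 40% and 50%. The 45% rate is added as an intermediate case.

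**Assumptions, not in the document:** two-sided alpha 0.05 (z = 1.960), equal arms, uncorrected chi-square (pooled two-proportion) test, no loss to follow-up. For 80% power, z = 0.8416.

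**Formulas**, with p1 the control rate, p2 = p1 − 0.15, and m = (p1 + p2)/2:

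- n per arm = [1.960·√(2m(1−m)) + 0.8416·√(p1(1−p1) + p2(1−p2))]² / d²
- power = Φ{ [d·√n − 1.960·√(2m(1−m))] / √(p1(1−p1) + p2(1−p2)) }

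**Step 1. Reproduce the plan's figure (40% vs 25%).** m = 0.325. √(2 × 0.325 × 0.675) = 0.6624 and √(0.2400 + 0.1875) = 0.6538. Then n = (1.2983 + 0.5503)² / 0.0225 = 151.9, so 152 per arm, as stated. Power at 152: (0.15 × 12.329 − 1.2983) / 0.6538 = 0.843, and Φ = 0.800.

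Other settings for 40% vs 25%: a continuity correction needs 165 per arm; one-sided 0.05 needs 120 (133 with continuity correction); unpooled variance needs about 150. Two-sided 0.05 without correction is therefore the natural reading.

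**Step 2. Keep the 15-point fall and move the control rate.** For 50% vs 35%: m = 0.425, √(2 × 0.425 × 0.575) = 0.6991 and √(0.2500 + 0.2275) = 0.6910. Power at 152 = Φ[(1.8493 − 1.3702) / 0.6910] = Φ(0.693) = 0.756. The other rows use the same formula.

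| Control vs test | Power, 152 per arm | Power, 162 per arm | n per arm for 80% |
|---|---|---|---|
| 35% vs 20% | 83.7% | 86.0% | – |
| 40% vs 25% | 80.0% | 82.5% | 152 |
| 45% vs 30% | 77.3% | 79.9% | 163 |
| 50% vs 35% | 75.6% | 78.2% | 170 |
| 57.5% vs 42.5% (worst case) | 74.6% | 77.3% | 174 |
| 70% vs 55% | 77.3% | 79.9% | – |
| 75% vs 60% | 80.0% | 82.5% | – |

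**Step 3. Range of failure at 152 per arm.** Power is below 80% for control rates of 40.1% to 74.9% (pooled), 40.4% to 74.6% (arcsine, and exact enumeration of the chi-square test) and 41.3% to 73.7% (unpooled). At 162 per arm the pooled range narrows to about 45% to 70%.

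**Step 4. Check by exact binomial enumeration.** At 152 per arm: 80.3% (40/25), 77.7% (45/30), 76.3% (50/35). At 162 per arm: 82.7%, 79.8%, 78.1%. The conclusion does not depend on the approximation.

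**Step 5. Try the setting most favourable to the plan.** With one-sided 0.05, power at 152 per arm is at least 83.7% for every 15-point fall, so the broad claim would hold. That setting needs only 120 per arm for 40% vs 25%, so it does not explain 152.

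**The case against.** The best reply is that the sizing case is both identifiable and correct. The fall from 40% to 25% and the enrolment target share one sentence, and that case gives 152. The 50% may be background for a differently worded group, in which case there is no contradiction and 50% vs 35% is not a case this trial faces. The broad power wording follows straight after the 40% to 25% hypothesis and may be loose phrasing for it. Alpha and sidedness are unstated, and a one-sided 0.05 test would rescue the claim. No control rate above 50% appears in the document, so the upper part of the failing range has little bearing here. Finally, this is a pilot, enrolment may reach 325, and the shortfall is a few points.

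Much of this stands. The 40% to 25% case is the sizing basis and should not be called wrong, the 50% vs 35% figures are conditional, and the practical effect is small. Three things remain. The 50% is still unexplained next to the 40%. The literal claim fails whichever group the 50% describes, since 45% vs 30% already falls short at 152 per arm. And the one-sided reading conflicts with the stated sample size. Being a pilot does not excuse a specific power figure that the design does not deliver.

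**Conclusion.** The concern holds. Two control rates stand unreconciled, and the power claim is too broad as written. At 152 per arm, a 15-point fall has less than 80% power for control rates between roughly 40% and 75%. Type II error is about 23% at 45% vs 30%. If the 50% rate applies to the powered comparison, it is about 24% at 152 per arm and about 22% at 162, against the implied figure of under 20%. The largest shortfall by the pooled formula is 80 − 74.6 = 5.4 points, at a control rate of 57.5%; at 50% it is 80 − 75.6 = 4.4 points.

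This rests on two-sided alpha 0.05 and an uncorrected chi-square test. Both are assumed, and both are supported by the match to 152. The design case of 40% vs 25% is sound but has no margin at 152 per arm. The point should be fixed, but it does not undermine the trial.

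**What to change.** In the Power Analysis of section 8:

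1. Say which control rate and which patient group the power statement rests on, and how the 50% and 40% figures relate.
2. Confirm and state alpha, sidedness and the test.
3. Delete the words that extend the power claim to any true difference.
4. If two-sided 0.05 and an uncorrected chi-square test are confirmed, restate as follows:

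> 152 per arm gives about 80% power to detect a fall from 40% to 25%; if the control rate is 50%, power for 50% vs 35% is about 76% (about 78% with 162 per arm).

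The cost is a wording change and a slightly less favourable stated power. No extra patients are needed and the conduct of the trial does not change.
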